5.2.4 Safety Endpoints

- Frequency of adverse events

6 PARTICIPANT SELECTION AND ENROLLMENT

6.1 Source of Participants

Subjects who meet the inclusion and exclusion criteria will be eligible for participation in this study following appropriate informed consent obtained from subject or subject’s legal representative and written approval from their primary care provider. Since nearly all patients with prediabetes are treated in the primary care setting, participants will be recruited from primary care practices in the University of Colorado network, as well as through advertisement on websites, emails, social media, and other IRB approved modalities. Individuals generally will be recruited from the site’s existing patient population or from a pool of individuals who contact the site. IRB requirements regarding recruitment materials and policies will be adhered to. Study recruitment methods may consist of the following:

- Use of Health Data Compass/TriNetX
- Culling of pre-existing databases of patients who have expressed interest in research participation. Those identified will be contacted via IRB-approved mailing sent through post, email blast, or via phone and will be provided information about how to complete the consent process and demographics survey;
- Support groups, patient education classes, and not-for-profit community support groups;
- IRB-approved paper and digital advertisements, brochures, postcards, flyers, and/or newsprint advertisements;
- IRB-approved digital advertisements posted on social media sites like LinkedIn, Twitter, YouTube, Instagram, Facebook, and other public forums managed by a clinical trial site;
- In-person recruitment and telephone recruitment by individual clinical sites; and
- An IRB-approved website dedicated to clinical trial recruitment.
- Letters/Emails to, phone calls with, or visits with area physicians informing them of the study and asking them to refer any eligible patients who might be interested

All recruitment methods and specific advertising materials will be IRB approved prior to their implementation. No individuals will be excluded based on gender or race. An equal gender distribution is anticipated.

6.2 Number of Participants

A total of up to 70 participants, with 20-24 anticipated to complete GEM due to trial design anticipating 50% of RC participants will want/be able to cross over to the intervention group and eligibility criteria.

6.3 Inclusion Criteria

- Adults between the ages of 25-70
- A1C of 6.0-6.4
- Documented diagnosis of prediabetes
- Have a smart phone
- Read English, as GEM currently only available in English
- Willing and able to follow the study procedures as instructed
- Having written approval by primary care provider

6.4 Exclusion Criteria

- Diagnosis of diabetes mellitus
- Currently taking any diabetes medication
- Currently taking a chronic medication that would interfere with metabolic control, such as prednisone
- Has a condition that precludes a low carbohydrate diet, such as gastroparesis
- Has a physical or medical condition that precludes walking 120 steps per minute, for 10 minutes or longer.
- Has kidney disease.
- Active or planned cancer treatment.
- Those who cannot speak English.
- Extreme visual or hearing impairment that would impair ability to use real-time CGM
- Subject is pregnant or anticipates becoming pregnant in the next 4 months.
- Subject anticipates moving within the next 4 months.
- Treating physician, for any reason, considering their patient inappropriate for the study, like uncontrolled bipolar disease

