Primary Objective	To determine if individuals with prediabetes can use GEM plus Libre CGM to improve metabolic control.

Primary Endpoints	Pre-post reduction in percentage of CGM readings > 120 from blinded pre-post LibrePro; additional outcomes of particular interest include, A1C and BG variability
Secondary Objectives	
 (1) To determine if individuals with prediabetes can use the GEM manual with Libre CGM to improve other clinical, psychosocial, and behavioral outcomes. (2) To explore psychological (readiness to change) and physiological (proteomics) measures. (3) To generate user feedback about improving the intervention.
Secondary Endpoints	
 (1) Endpoints will include psychosocial scales, basic demographic information, comparative labs, Steps, Hours Active, or Active Minutes. (2) Analysis of individual proteins and protein pathways measured through use of a multiplex proteomics platform. (3) Endpoint will include the Program Importance Questionnaire
Participation Criteria	
Inclusion Criteria:
 
 • Age 25-70 years • A1C 6.0-6.4 • Documented diagnosis of prediabetes • Have a smart phone • Able to read English, as the GEM guide is currently only available in English • Willing and able to follow the study procedures as instructed 
Exclusion Criteria:
 
 • Diagnosis of diabetes mellitus • Currently taking any diabetes medication • Currently taking medication that promotes insulin resistance or otherwise interferes with metabolic control (e.g. prednisone) • Has a condition that precludes a low carbohydrate diet, such as gastroparesis • Has a physical or medical condition that precludes walking 120 steps per minute, for 10 minutes or longer • Has documented kidney disease that would preclude participation in study per PI discretion • Active or planned cancer treatment. • Extreme visual or hearing impairment that would impair ability to use real-time CGM • Pregnant or anticipates becoming pregnant in the next 4 months. • Anticipates moving within the next 4 months. • Treating physician, for any reason, considers their patient inappropriate for the study (e.g. uncontrolled bipolar disease)
Sample Size	Up to 70 screened participants with prediabetes and an A1c between 6.0-6.4 to provide a cohort of 36 enrolling in the trial, with a goal of at least 30 participants completing the trial.

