Description of Study Intervention	Blinded CGM data (obtained through the use of the Libre Pro) and blinded activity data (obtained through the use of a FitBit) will be obtained for 2 weeks on all participants at the start and end of the study, and baseline clinical data collection and psychosocial scales will be completed prior to randomization. The intervention group will be given Libre 2 supplies for 4 months, an activity monitor, and the 4-chapter GEM paper guide. The intervention group will complete a virtual or inperson study visit where they will receive instructions on how to apply their unblinded Freestyle Libre and connect it to the study account, as well as how to

	
register their Fitbit to the study account. If the visit will be conducted remotely, participants will be mailed their CGM, Fitbit, and the GEM manual. Participants will receive one telephone call to review use of the GEM Guide and call at two weeks and six weeks later when the probability of dropouts from lifestyle intervention peaks. Participants will follow the self-directed GEM guide for 4 months (a 1-month treatment period followed by a 3-month maintenance period) while wearing a FitBit activity monitor and a Freestyle Libre 2 CGM. Participants will be given this guide and a study email so they can easily ask questions about the GEM program during treatment. Fielding GEM questions will help the study progress smoothly and will gain information that might improve the Guide in the future. Relevant questions and corresponding answers will be posted on a study website for all participants to review, if desired. However, all medical management questions will be referred back to the participant's treating physician. The GEM Guide for Prediabetes contains the following information in four chapters: Glucose Impact of Routine Choices, Recovering from BG Excursions, Reducing BG Excursions, and Maintenance. The RC group will follow recommendations from their primary care physicians and clinicians that will be tracked for later analysis. RC participants will have the opportunity to receive the intervention four months after consenting and completing of the RC pre-post assessments. Comprehensive proteomics analysis will be done at the same time after all samples have been collected.

Study Duration	
This study will last approximately 24 months from the beginning of subject recruitment to data analysis.

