5.2.2 Primary Endpoint

- pre-post reduction in percentage of CGM readings >120, from blinded pre-post LibrePro.

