9.4 Visit 2/3– Start

9.4.1 RC Start (for participants randomized to RC), at least and as close as practical to 14 days following Secondary Baseline visit

1. History review, assess for AEs since last visit
2. Notify participant of randomization to RC
3. Blinded CGM data acquisition
4. Collect activity monitor
5. Schedule Follow Up visit for 4.5 months later (+/-2 weeks)
6. Schedule reminder contact for 2 weeks before next Visit; during contact, ask about interest in GEM if eligible

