9.6 Visit 4/5- Study Period 2 Start

1. History review, assess for AEs since last visit
2. Blinded CGM data acquisition
3. Instruct participant on unblinded Freestyle Libre 2 CGM
 - a. Instruct on placement, use, strongly encourage scanning 20-40 times a day, but at a minimum scanning at least every 8 hours
 - b. Ensure participant account is working
 - c. Connect to study account
4. Instruct participant on activity monitor
 - a. Instruct on use
 - b. Reconfigure smartphone settings to unblind activity date
 - c. Verify participant account connection to study account
5. Review the GEM manual and read Unit 1 to ensure the participant understands the program. Encourage to complete 4 daily diary logs. Encourage significant other (if applicable) to also be present. Document whether significant other is present. To accommodate individual learning styles this may be done anytime within 1 week of the GEM Start Visit.
6. Set up text messaging (content, timing, frequency)
7. Schedule follow-up contact 2 weeks and 6 weeks later (when probability of dropout from lifestyle intervention peaks). Assess satisfaction with text messaging and change content/timing/frequency if necessary (and document).
8. Schedule Follow-up Visit for 4.5 months later (+/-2 weeks)
9. Schedule reminder contact for 2 weeks before next Visit; at that time, contact participant to assure they have a Libre 2 sensor inserted to collect the 14 days of end of study data.
10. Optional: For any participant coming off of the intervention, they will be asked at the end of the study visit 4 or 6, or contacted by email, phone, and/or letter to discuss if they would like to complete a short, semi-structured interview via audio and/or audio and video to provide feedback on the intervention to assist in improvements with the program for future studies. The interviews will be recorded and participants will be made aware of this. If any PHI is mentioned during the interview, it will be removed during the transcription process. This part is not required as part of the intervention and will not affect compensation or any study procedures.

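### The pregnancy and relocation exclusions look 4 months ahead, but the schedule puts the whole post-assessment, including the blinded CGM recording for the primary endpoint, at about 5 to 5.5 months after consent

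*Combined protocol and SAP*

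**What the plan says.** **The look-ahead.** Section 6.4 has two time-limited exclusions: "Subject is pregnant or anticipates becoming pregnant in the next 4 months" and "Subject anticipates moving within the next 4 months". The Protocol Summary (Section 2) has the same horizon, for example "Pregnant or anticipates becoming pregnant in the next 4 months".

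**The endpoint.** Section 5.2.2 defines the primary endpoint as "pre-post reduction in percentage of CGM readings >120, from blinded pre-post LibrePro". According to the Protocol Summary, the blinded data "will be obtained for 2 weeks on all participants at the start and end of the study".

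**The schedule.**
- The Start visit comes "at least and as close as practical to 14 days following Secondary Baseline visit" (Section 9.4.1). Appendix 1 gives 14 days with a 2-day tolerance.
- At RC Start the instruction is "Schedule Follow Up visit for 4.5 months later (+/-2 weeks". GEM Start (Section 9.4.2) has the same interval.
- The blinded post sensor is handed over (RC, Section 9.5.1) or placed (GEM, Section 9.5.2) at that end visit, and is mailed back afterwards.
- For crossovers, Section 9.6 repeats "Schedule Follow-up Visit for 4.5 months later (+/-2 weeks", and Section 9.7.1 again places a blinded sensor at the end visit.

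**The competing timeline.** The Protocol Summary describes a 4-month GEM course, and both it and Section 5.1 offer crossover four months after consent. The Group 2 description in Section 5.1, the opening of Section 9, Sections 9.4.1 and 9.4.2, and Appendix 1 all use 4.5 months.

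**The concern.** A screening question with a time limit is useful only up to that limit. Here it expires before any post-assessment takes place. Someone who expects to conceive or move in month 5 is not caught by either criterion, yet the end visit and the blinded recording fall at that time or later.

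At stake is post data that one screening question could have protected: the blood draw with A1c and proteomics, weight, the scales, and possibly the post CGM recording, because the sensor is supplied at the end visit. Pregnancy is a listed possible reason for stopping study treatment (Section 10.4.1). Withdrawn subjects are not replaced (Section 10.4.3). Section 11.1 includes all randomized subjects, but Section 11 does not say how missing post values will be handled.

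**Working it through.** The plan gives no derivation of the 4 months, so the check compares it with the plan's own visit intervals. One month = 365.25/12 = 30.44 days, so 4 months = 121.8 days and 4.5 months = 137.0 days. Day 0 is consent and baseline at Visit 1.

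**1. Period 1, as scheduled**

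| Event | Formula | Nominal | Earliest | Latest |
|---|---|---|---|---|
| Look-ahead ends | 4 × 30.44 | day 122 | – | – |
| Start visit | 14 ± 2 | day 14 | 12 | 16 |
| End visit, post sensor supplied | Start + 137 ± 14 | day 151 | 135 | 167 |
| Post recording complete | end visit + 14 | day 165 | 149 | 181 |

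The shortfall at completion is 165 − 122 = 43 days nominally, with a range of 149 − 122 = 27 to 181 − 122 = 59. In months from consent, completion falls at 165/30.44 = 5.42 (4.89 to 5.95). Even the earliest end visit, day 135, is 13 days past the look-ahead. Participants who need the Secondary Baseline visit start later by an unstated interval, which widens the gap.

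**2. Readings more favourable to the plan**
- *Question re-asked at Start.* Appendix 1 has an eligibility check there. Counted from Start, the look-ahead ends at day 122 and the recording runs over days 137 to 151. With the end visit two weeks early it begins at 137 − 14 = day 123, still past the limit, though by only about a day. This check also comes after randomization.
- *4.5 months counted from baseline.* The numbers are the same: days 137 to 151 nominally, with the earliest sensor placement at day 123 (4.04 months).
- *GEM data from the 14 days before the end visit* (the Libre 2 reminder in Section 9.4.2). These run over days 137 to 151 nominally, also outside. With every window at its earliest they would begin at 135 − 14 = day 121, level with the limit. They are not the LibrePro recording named in the endpoint.

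**3. Coverage of the intervention itself.** A 4-month GEM course that begins on day 14 ends at 14 + 122 = day 136. Counted from consent, the look-ahead does not cover that either.

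**4. Crossover.** From Visit 4/5, GEM End is at 137 days (123 to 151) and the recording is complete at 151 days (137 to 165), or 4.96 months (4.50 to 5.42). From consent, completion is at about 165 + 137 + 14 = day 316, or 10.4 months. Only a question asked afresh at crossover can cover this period.

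**5. Room for loss.** With 36 enrolled and a goal of 30 completers, six losses are affordable (6/36 = 16.7%). At the upper attrition allowance in Section 5.1, 36 × 0.80 = 28.8 would complete, already below 30.

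**The case against.** The day count is hard to dispute. The objections concern purpose and consequence.

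- **Purpose is not stated.** No section says what these exclusions protect, and 4 months matches the stated length of the GEM course. That explains where the figure comes from. It does not rescue it, because 4 months from consent ends about two weeks before a course that starts on day 14. Protecting the post-assessment remains an inference.
- **Other criteria give discretion.** Section 6.3 requires that participants be willing and able to carry out the procedures and have primary care approval, and Section 6.4 lets the treating physician object. Someone with a firm relocation plan might be declined on these grounds. This stands in part, but nothing prompts the site to ask about month 5.
- **Direct loss of the primary endpoint.** A reader might infer that each such case removes a primary endpoint value. The documents do not support this. Sensors are returned by mail, a move may be local, and Section 10.4.1 treats pregnancy as a possible reason for stopping treatment while encouraging those who stop to complete the remaining visits. What survives is narrower: someone who misses the end visit loses the blood draw and may not receive the post sensor.
- **The crossover check.** A reader might infer that Visit 4/5 repeats a 4-month horizon. Appendix 1 conditions crossover only on still being eligible and does not say which questions are asked or how far ahead they look.
- **Scale.** This is a pilot without a formal power analysis, it already allows for up to 20% attrition, and few people will have such plans in a gap of one to two months. This stands and limits the weight of the point.

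**Conclusion.** The point holds as a mismatch between two eligibility criteria and the trial's own schedule. The blinded post recording lies wholly beyond the 4-month look-ahead under every reading tried, and the shortfall at completion is 27 to 59 days from consent. The tightest reading, a re-check at Start followed by an end visit two weeks early, leaves a margin of only about a day at sensor placement.

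The practical effect is probably small and cannot be quantified: the documents do not say how many people plan a move or pregnancy in that interval. Nor can a loss be expressed as a share of an arm. A reader might assume 18 per arm, but Section 5.1 says allocation began at 2:1 and later changed to 1:1 (Section 7.1.1 still gives 2:1), so final arm sizes are not stated.

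The conclusion assumes that the criteria are applied at Visit 1, that the post sensor is worn for 14 days from the end visit, and that the exclusions are meant to protect the post-assessment. The probable root cause is the unreconciled use of 4 and 4.5 months. The change is worth making because it is cheap and the trial has little slack.

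**What to change.** 1. Reconcile the 4-month statements (Protocol Summary and the crossover text in Section 5.1) with the 4.5-month statements (Group 2 in Section 5.1, the opening of Section 9, Sections 9.4.1, 9.4.2 and 9.6, and Appendix 1). Which timeline applies is for the sponsor to settle.
2. In the Protocol Summary and Section 6.4, tie both criteria to an event: the look-ahead runs to completion of the post-assessment blinded CGM recording. Add a month figure derived from the reconciled schedule. As the schedule now stands, that is about 5.5 to 6 months from consent.
3. In Section 9.6 and Appendix 1, state that both questions are asked again at Visit 4/5 and look to the end of the period 2 post recording, about 5 to 5.5 months from that visit.

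The cost is a change to two criteria and the prescreen script, a protocol amendment with prior IRB approval (Section 13.1), and perhaps a few more screen failures within the 70 allowed. The trial is under way, so the change helps only people not yet enrolled or crossed over, and those enrolled before and after it will have been screened under slightly different wording. The report should say so.

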6.5 Concomitant Medications

For this protocol, a prescription medication is defined as a medication that can be prescribed only by a properly authorized/licensed clinician. Medications to be reported in the Case Report Form (CRF) are concomitant prescription medications, over-the-counter medications, and supplements.

6.5.1 Prohibited Medications and Treatments

Patients will be excluded if currently taking a chronic medication that would interfere with metabolic control, such as prednisone. Patients will be excluded if currently taking any diabetes medication prior to enrollment in the study. They will be allowed to continue if treatment is started after enrollment, but will be documented.

7 STUDY TREATMENTS

7.1.1 Method of Assigning Subjects to Treatment Groups

2:1 Randomization; in previous studies baseline metrics have not been found to influence outcome, other than very high A1c, which is not applicable to this study.

7.2 Description of GEM

The 4-chapter GEM paper guide provides: 1) decisive didactic information about the effects of net carbohydrate consumption and routine physical activity on blood glucose fluctuations; 2) instructions to systematically use CGM feedback to *educate* them about how carbohydrates and physical activity impact *their* BG excursions, *motivate* them to repeat choices that lead to lower AUC, *activate* them to take steps to lower their BG elevations when detected by the high glucose alarm, and *investigate* the BG impact of new food and activity choices concerning their effect on their BG; 3) employ structured self-monitoring (diary) to organize and identify personal patterns in their food and physical choices that impact their AUC, and 4) automated personalized daily text messages to encourage engagement in a GEM lifestyle.

7.3 Devices

The FreeStyle Libre 2 Flash Glucose Monitoring System is a continuous glucose monitoring (CGM) device with real time alarms capability indicated for the management of diabetes in persons age 4 and older. It is intended to replace blood glucose testing for diabetes treatment decisions, unless otherwise indicated. The System also detects trends and tracks patterns and aids in the detection of episodes of hyperglycemia and hypoglycemia, facilitating both acute and long-term therapy adjustments. Interpretation of the System readings should be based on the glucose trends and several sequential readings over time. The System is also intended to autonomously communicate with digitally connected devices. The System can be used alone or in conjunction with these digitally connected devices where the user manually controls actions for therapy decisions.

Use of the FreeStyle Libre 2 Flash Glucose Monitoring System in this protocol complies with the requirements for a non-significant risk study under 21 CFR 812.3(m). It is not an implantable device, it is not represented to support or sustain human life, is not for use in diagnosing, curing, mitigating or treating disease and use of the device does not present a serious risk to study subjects. It is stored at room temperature.

The FitBit Activity Monitor is an FDA cleared device that will be used in this study to measure outcome data. It is stored at room temperature.

8 STUDY PROCEDURES AND GUIDELINES

A Schedule of Events representing the required testing procedures to be performed for the duration of the study is diagrammed in Appendix 1. To allow for individualized learning styles, a participant may choose to conduct the “Review

the GEM manual and Read Chapter One” at a different time than the rest of the GEM Start Visit, but within 1 week of the GEM Start Visit.

Prior to conducting any study-related activities, written informed consent and the Health Insurance Portability and Accountability Act (HIPAA) authorization will be signed and dated by the subject.

